1.2.2 RATIONALE FOR SELECTION OF SUBJECTS BY RACE

PCa has the largest health disparity for any cancer site in the US (52). The causes of this health disparity are multifactorial and may include tumor biology. African-American men have the highest incidence and mortality rates. The disease accounts for about 39% of all cancers diagnosed in African-American males (53). The age-adjusted African-American to Caucasian cancer incidence ratio is about 1.6 but the mortality rate is 2 to 3-fold higher for African-Americans than Caucasians (22). African-American men develop PCa at a younger age, and the disease progression is faster than in Caucasians (22). It is hypothesized that the tumor biology of PCa is different in the two ethnic groups.

1.2.3 RATIONALE TO STUDY ALLELE VARIANT GENES AS RISK FACTORS IN PROSTATE CANCER

Allele variant genes belong to the category of low penetrance susceptibility genes (54). A mutation in a low penetrance gene does not cause cancer but contributes to cancer risk, and affects large segments of the population. The investigation of allele variant genes will provide clues to the role of genetic risk factors in nonhereditary cases. Further, the identification of low penetrance susceptibility genes can have important public health implications.

The association between allele variant genes and cancer risk has been studied extensively (55-57). Only a small number of disease-associated allele variants have been identified at this point. There are various reports on PCa susceptibility as it relates to low penetrance susceptibility genes (58,59). Polymorphisms in cell cycle genes, such as cyclin D1, CDKN1A, and CDKN1B, have been studied and an association between some allele variants and an increased PCa risk has been reported (60,61). Most of the epidemiological studies focused on genes in the androgen pathway. CYP17 is a key enzyme in the synthesis of sex hormones. A polymorphism in this gene is associated with an increased cancer risk in African-American men, but not in Caucasians, as suggested by several reports and confirmed by a recent meta-analysis (62). Testosterone is irreversibly converted to dihydrotestosterone (DHT) by the enzyme steroid 5α -reductase

NCI IRB Approval:	October 28, 2004
Protocol Number:	05-C-N021

type II (SRD5A2). The conversion to DHT is a major modulator of androgenic activity. Thus, SRD5A2 polymorphisms that modulate the bioavailability of DHT have been studied as risk factors in PCa. A SRD5A2 polymorphism, Ala49Thr, has been found to be associated with markers of poor prognosis or cancer risk (63,64), and a frequency gradient of another polymorphism, Val89Leu, in the SRD5A2 gene exists among racial/ethnic groups, which parallels PCa risk (65). However, a more recent meta-analysis of the published literature did not support an association between SRD5A2 genotypes and PCa risk (66). A variant polyglutamine tract in the androgen receptor gene (67,68) has also been studied, but the association with cancer risk is rather inconsistent. Recently, a joint effect of two polymorphisms in the 3β -hydroxysteroid dehydrogenases I and II has been observed. Men with the two variant genotypes had a significantly higher risk to develop PCa. A relative risk of 2.6 to 3.1 for hereditary and sporadic PCa was observed among carriers with the two mutant alleles (39).

[figure not shown]
Another essential pathway in prostate carcinogenesis is tumor angiogenesis. Recent publications point to the potentially great importance of allele variant genes in the angiogenesis pathway for PCa progression (Table 3). A single nucleotide polymorphism in the angiogenesis inhibitor, endostatin, has been found to predispose to PCa (69). The Asp1437Asn polymorphism is located in a conserved region and, presumably, inhibits protein function. Furthermore, two genetic variants that reduce the promoter activity of two pro-angiogenic factors, interleukin-8 and VEGF, were found to be significantly less frequent in PCa patients than in a control population (70). Lastly, a polymorphism in the endothelial nitric oxide synthase, Glu298Asp, was found to be significantly more common among cancer patients with an advanced disease than in the control population (71). The data indicate that inherited PCa susceptibility may be partly explained by genetic traits in genes of the angiogenesis pathway.

Table 3: Allele Variant Genes of the Angiogenesis Pathway as Risk Factors for Prostate Cancer			
Gene	Variant Allele	Rare or Mutant Allele Frequency (%)	Reported Risk Association (mut versus wt)
Interleukin-8	A(-251)T	50	OR 0.66 95% CI (0.44 - 0.99)
VEGF	G(-1154)A	30	OR 0.45 95% CI (0.24 - 0.86)
eNOS	Glu298Asp	40	OR 2.1 95% CI (1.12 - 4)
Endostatin	Asp1437Asn	5-10	OR 2.4 95% CI (1.4 - 4.16)

Our goal is to study the modulation of PCa risk by allele variant genes that regulate five distinct pathways. We will explore genetic susceptibility that is driven by 1) host defense, 2) chronic inflammation, 3) hormone-stimulated survival and proliferation

NCI IRB Approval:	October 28, 2004
Protocol Number:	05-C-N021

of mutant cells, 4) an impaired DNA repair capacity, and 5) tumor angiogenesis. We will analyze genotype-risk associations in the context of race and the environment because dominant gene effects without environmental involvement are unlikely to occur. We will also determine associations between genotypes and poor prognosis markers. An allele variant that is associated with cancer risk will be further validated to establish biological plausibility and mechanisms of causality (Table 4). The additional verification steps, as shown in the table, are important to minimize the possibility of a false positive relationship between a genotype and cancer risk. These experiments will provide important mechanistic information. Disease-associated genotypes will subsequently be validated in larger studies.

1.2.4 RATIONALE TO STUDY MOLECULAR PROFILES OF PROSTATE CANCER

Current therapeutic approaches to treat advanced stages of human PCa are palliative rather than curative. In the majority of cases, an aggressive cancer ultimately becomes androgen-refractory resulting in the death of the patient. There is an immediate need to prevent the progression of the clinically localized disease by increasing the understanding of the basic biology of PCa. The propensity for disease progression is different for African-Americans and Caucasians and may define the strong ethnic differences in PCa mortality (53). A critical challenge is to develop means that distinguish indolent cancers from those that are potentially lethal. The application of gene expression profiling to study PCa has resulted in significant successes, including the identification of novel clinical markers that improve tumor classification and the prediction of outcome (72).

The genetics of PCa are poorly understood (73). Oncogenically activated RAS is common in some types of cancer, but the underlying mutations that lead to the activation

NCI IRB Approval:	October 28, 2004
Protocol Number:	05-C-N021

are rarely found in prostate tumors (74). Mutations in the p53 tumor suppressor gene are more common, and approximately one third of advanced prostate carcinomas have either a mutated p53 or over-express a functionally inactivated p53 protein (75). Germline mutations in the ribonuclease L (RNASEL) gene have been associated with hereditary PCa (76), and the common Arg462Gln allele variant may have a major role in the development of some PCa (77). Other putative tumor suppressor genes are located on chromosomes 8p, 10q, 13q, and 17p (73). Two candidate susceptibility genes at chromosome 8p and 17p have been described (78,79). The genes, macrophage scavenger receptor 1 (MSR1) and ELAC2, were found to be associated with PCa in high-risk families and two allele variants in the MSR1 gene were found to be weakly associated with PCa risk in African-American men (80). However, a molecular mechanism that could explain the aggressive nature of PCa in African-Americans has not been established.

Recent progress in whole genome expression profiling has generated prognosisrelated molecular profiles for many cancer types (81-83). A four-gene expression model has been described that discriminated between seven PCa patients with relapse and seven PCa patients without relapse, independently of stage and grade (84). The gene expression profiles were obtained from clinically localized tumors that were removed by radical prostatectomy. Another research group studied a group of 23 PCa patients, who were treated with adjuvant androgen suppression therapy before surgery (85). The surgical specimens were investigated for correlations between a patient's gene expression profile and disease recurrence with a 5-year follow-up. An eight-gene signature was identified that classified patients into a PCa recurrence group and a non-recurrence group with an overall correct prediction of 83%. A combination of gene profile and clinical/pathological parameters yielded a correct prediction of 96%.

Although these investigations have shown that gene expression profiles can predict PCa recurrence, there is no such study in the literature that has attempted to identify the genes and pathways with relevance to the etiology and aggressive behavior of PCa in African-Americans. Our objective is to find molecular signatures of low-stage and high-stage tumors in African-Americans, and to identify genes that are relevant to metastasis and patient outcome. The research is also aimed at determining molecular profiles in the context of lifestyle and diet if a strong association between a lifestyle/dietary component and cancer risk has been reported or can be established in our study population. We expect to collect up to 100 fresh-frozen tumor specimens that 1) are primarily identified by PSA screening, 2) are positive for cancer by needle biopsy, and 3) are surgically removed by radical prostatectomy. Of those, we expect that about 25% of the patients will have an advanced pathological stage (\geq pT3) or a Gleason score \geq 7 (86). Of the 52 patients, who underwent radical prostatectomy at the 2 participating hospitals in 2001, 49 were informative for staging and 24.5% of these had an advanced pathological stage (Table 5).

We will investigate gene expression patterns in both tumor tissue and the surrounding non-tumor tissue. We will develop gene expression profiles of 60-100 microdissected tumors (Table 6). We hypothesize that gene products of both tumor and stromal cells drive tumor progression and the invasion of normal surrounding tissue. We will use laser-captured microdissection to separate tumor from normal tissue, and to determine the molecular profiles that separate 1) PCa in African-Americans from PCa in Caucasians, 2) high pathological stage from low pathological stage tumors, and 3) poor

NCI IRB Approval:	October 28, 2004
Protocol Number:	05-C-N021

from good outcome. Candidate marker genes for tumor progression and outcome will be validated by quantitative PCR, and will be further studied.

 Table 5: Stage Distribution of 49 PCa Patients Undergoing Radical Prostatectomy at the Two Participating Hospitals

Calendar Year 2001	
Pathological Stage	Number of Patients
Stage I + II	37
Stage III	11
Stage IV	1

Table 6: Tumors for Expression Profiling Stratified by Race and Pathological Stage

Race	Pathological stage	Number of specimens
African-American	Low (pT2)	20-30
	High (pT3)	10-20
Caucasian	Low (pT2)	20-30
	High (pT3)	10-20

1.2.5 RATIONALE TO STUDY ASSOCIATIONS BETWEEN IGF-1 AND TUMOR MARKERS

Westernization is a major risk factor for PCa. A Western-style diet increases IGF-1 blood concentrations and PCa risk (6,87). Deregulated expression of IGF-1 in the prostate epithelium leads to neoplasia in transgenic mice (88). More recent data have shown that IGF-1 induces the activation of the Akt pathway, inhibits apoptosis, and up regulates VEGF expression (89). Akt is a tumor oncogene that is activated by phosphorylation (90). It is anti-apoptotic and induces a survival response in cells (91,92). We will test the hypothesis that a high IGF-1 bioavailability promotes PCa by activating the Akt pathway in prostate tissue. We will measure plasma IGF-1 and IGFBP3 protein concentrations and correlate IGF-1 bioavailability with tissue markers of Akt activation, such as phosphorylated Akt, phosphorylated target genes of Akt (e.g., eNOS, caspases, Bad, IKK), apoptotic index, expression of VEGF and COX2, and tumor microvessel density. We will also explore whether a diet high in allium vegetables, which has been shown to reduce PCa risk (11), is an inhibitor of the IGF-1 pathway.

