The reasons for the large racial and geographic differences are poorly understood but both environmental and genetic risk factors are thought to be involved. Migrant studies support the involvement of environmental factors (2-4). The adoption of a Western-type diet has been found to strongly increase the risk for PCa (5,6). High meat and animal fat intake, and excessive alcohol consumption, correlate positively with PCa risk (7-9), while a diet that is either high in phytoestrogens (10), such as a soy diet, or in allium vegetables (11) appears to be protective. Although smoking does not appear to be associated with the incidence of PCa (12,13), an association between current smoking and high grade or metastatic PCa has been reported (14-17). It suggests that smoking promotes the progression to a more advanced disease. Other observations point to the role of genetic susceptibility factors in human PCa. The lifetime risk of PCa increases 1.5 to 4-fold in men with one or two first-degree relatives with PCa (18). A Scandinavian study of twins estimated that 42% (95% CI: 29% - 50%) of the observed PCa susceptibility was associated with inherited genetic risk factors (19). Genetic risk factors are particularly significant at a younger age, and the attributable risk of inherited susceptibility is thought to be as high as 30%-40% among men diagnosed with PCa at age 55 years or younger (18). The importance of genetic susceptibility is further suggested by the finding that only humans and dogs, but not other mammals develop PCa (20). Recent reports indicate that PCa biology is different in African-Americans when compared with Caucasians. African-American men develop higher stage carcinomas earlier in life than Caucasian men (21). It appears that both an earlier onset and a more rapid progression of the disease in African-Americans contribute to the difference in mortality between the two ethnic groups (22). Such observations are supported by additional data. The Prostate Cancer Outcomes Study concluded that traditional socioeconomic, clinical, and pathologic factors, could not explain the increased risk of advanced-stage PCa in African-American men (23). Autopsy examination of prostate specimens revealed that the frequency of small latent carcinomas is similar in low-risk and high-risk populations (4,24). In contrast, larger and highergrade carcinomas are more common in high-risk than in low-risk populations, and the frequency correlates with the incidence of clinical PCa. The data show that genetic and/or environmental factors modulate the progression from a small, microscopic carcinoma into a large carcinoma (4,25), and that tumor progression is the critical step that defines the strong ethnic differences in PCa risk and mortality.

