Non-androgenic mediators of prostatic growth have been described. A high blood concentration of insulin-like growth factor-1 (IGF-1) has been associated with an increased risk of advanced PCa (36-39). Insulin resistance, and chronically high insulin blood concentrations, are also predictors of increased cancer risk (40,41). The increased secretion of IGF-1 and insulin appears to be linked to a Western-style diet, a known risk factor for PCa. Other data suggest that several endothelial-derived factors and mediators of inflammation, such as interleukin-6 and -8, endothelin-1, vascular endothelial growth factor (VEGF), eicosanoids and nitric oxide, contribute to PCa progression (42-48). Mediators of inflammation, such as eicosanoids and nitric oxide, have also proangiogenic properties and induce functional changes in the vasculature that will lead to vessel remodeling, stimulation of endothelial cell mitosis and vessel growth. Overexpression of cyclooxygenase-2 and nitric oxide synthase-2 in human PCa has been reported (48-51). Chronic inflammation of the prostate may, therefore, promote cancer progression through the angiogenesis pathway.

NCI IRB Approval: Protocol Number: October 28, 2004 05-C-N021

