3.1.1 QUESTIONNAIRE

Trained interviewers will administer the questionnaire. The interview will last approximately one hour. The questionnaire assesses prior medical and cancer history, tobacco use, dietary risk factors, current medications, occupational history, medical

NCI IRB Approval:	
Protocol Number:	

October 28, 2004 05-C-N021

history and family medical history, socioeconomic status, anthropometry, and sexual history. The sexual history section is self-administered. This questionnaire is shared with the lung study and contains question relevant to both prostate and lung cancer.

INTERVIEWER TRAINING

The interviewers will receive a procedure manual. They will be trained in how to identify eligible subjects, how to provide informed consent, how to administer and properly complete the questionnaire, how to perform phlebotomy, and how to properly process blood and urine samples. The field supervisor will provide the training. Newly hired interviewers will practice the administration of the questionnaire to office volunteers. Interviewers will then administer the questionnaire and draw blood from subjects under the supervision of the field supervisor, who will provide feedback after the interview.

STEPS TO BE TAKEN IF A PATIENT BECOMES EMOTIONALLY UPSET DURING THE INTERVIEW PROCESS

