wild-type genotype (major allele), or the lowest exposure subgroup, as the reference group. Odds ratios and 95% confidence intervals will be calculated by unconditional logistic regression. Regression analysis will be performed in univariate and multivariate models to assess associations between risk factors and cancer susceptibility, and to adjust for possible confounding factors. Case-case analyses, correlating tissue marker expression with tumor staging, hormone blood concentrations, diet or genotypes, will be done by ANOVA, with the student's t-test, or a nonparametric test, such as the Mann-Whitney U rank sum test. To look at trends, the Mantel-Haenszel test for trend will be used to assess the correlation between marker expression/frequency and categorized (e.g., low, medium, high) variables, such as tumor stage, intake of a dietary factor, or IGF-1 blood concentrations. The association between a genotype and outcome will be studied either in a logistic regression model after categorizing into a good and poor outcome group or with the Kaplan-Meier method and the log-rank test. All analyses will be performed with the STATA and SAS statistical software packages.

ANALYSIS OF GENE EXPRESSION PROFILES

The data from the Affymetrix HG-U133A array will be estimated using the RMA procedure from Bioconductor (www.bioconductor.org). Previous analysis on raw data from replicate samples with RMA indicates that the mean standard deviation of log2 intensities is 0.1 across all intensity levels. This corresponds to a typical technical error of 5%-10% (94).

The factorial study design suggests an analysis of variance. We will first examine the four groups for heterogeneity of variances by comparing the ratios of variances between groups to the F-distribution. If the distributions conform, we will follow standard ANOVA procedure. If there is significant departure from agreement, we will perform non-parametric ANOVA using the rank F-test and use the Welch t-test for two group comparisons. We will select differentially expressed genes for contrasts between racial groups at each level of tumor, and for the difference between tumor stages across racial groups. To address the multiple comparisons problem we will use a modified FDR procedure of Benjamini and Hochberg adapted to correlated data (95).

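### The tests named for diet against tissue markers carry no adjustment for a Western-style diet, so an apparent allium effect on the IGF-1 pathway could be a dietary-pattern artefact

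*Protocol*

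**What the plan says.** Only the protocol is at hand.

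- **The question.** Section 1.2.5 (rationale for IGF-1 and tumor markers) ends: "We will also explore whether a diet high in allium vegetables, which has been shown to reduce PCa risk", is an inhibitor of the IGF-1 pathway.
- **The competing explanation.** The same section states: "A Western-style diet increases IGF-1 blood concentrations and PCa risk". The Introduction agrees: "The increased secretion of IGF-1 and insulin appears to be linked to a Western-style diet, a known risk factor for PCa". It also reports, on diet and risk, "High meat and animal fat intake, and excessive alcohol consumption, correlate positively with PCa risk", and in the same sentence lists allium vegetables as apparently protective.
- **The tests.** Section 5.4.3 says: "Case-case analyses, correlating tissue marker expression with tumor staging, hormone blood concentrations, diet or genotypes, will be done by ANOVA", the t-test or a rank test such as Mann-Whitney. A Mantel-Haenszel test for trend relates marker expression to categorized variables; intake of a dietary factor and IGF-1 concentration are among the examples. No covariate or stratification factor is named for either.
- **Where adjustment is planned.** Section 5.4.3 also plans multivariate regression to deal with confounding, but for risk factors against cancer susceptibility.
- **The data.** Section 3.1.1: "The questionnaire assesses prior medical and cancer history, tobacco use, dietary risk factors", and further on anthropometry. The questionnaires are attachments and are not shown.

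**The concern.** Whether a food inhibits a pathway is a causal question, and the comparison is between men who chose their own diets. The protocol itself names another dietary feature that raises IGF-1. If high allium intake goes with a less Western diet, a comparison of markers across allium groups mixes the two. The error has a direction: it lowers the apparent activity of the pathway in high-allium men, which is the result the hypothesis expects. Frequency matching on age and race does not help, because it balances cases against controls and not diet groups among the cases.

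At stake is a mechanistic statement about allium vegetables that may describe overall dietary pattern instead.

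**Working it through.** The protocol gives no sample-size or power figure for this question, so there is nothing to reproduce. The check has two parts.

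**1. What the text fixes**

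| Comparison | Method in section 5.4.3 | Adjustment named |
|---|---|---|
| Risk factors vs cancer susceptibility | Univariate and multivariate regression | Yes |
| Tissue markers vs diet or hormone levels | ANOVA, t-test, rank test | None |
| Trend of markers over dietary intake or IGF-1 category | Mantel-Haenszel trend | None |
| Allium intake vs blood IGF-1 | No method named | – |

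**2. How large the artefact could be for tissue markers**

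Inputs:
- Number of tumors: 60 to 100 are to be profiled (section 1.1). I take n = 80, the midpoint.
- Correlation of allium intake with Western diet: -0.2 to -0.4. Assumed; not in the documents.
- Correlation of Western diet with the marker: 0.1 to 0.3. Assumed; not in the documents.
- True allium effect: zero. Two-sided alpha 0.05.

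Formulas:
- spurious r = r(allium, Western) × r(Western, marker)
- d = atanh(|r|) × √(n − 3)
- rejection rate = Φ(d − 1.96) + Φ(−d − 1.96)

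Results for n = 80, where √77 = 8.775:

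| Assumed pair | Spurious r | d | Rejection rate |
|---|---|---|---|
| no allium–Western correlation | 0 | 0 | 5.0% |
| -0.2 × 0.1 | -0.02 | 0.176 | 0.0372 + 0.0164 = 5.4% |
| -0.3 × 0.2 | -0.06 | 0.527 | 0.0759 + 0.0064 = 8.2% |
| -0.4 × 0.3 | -0.12 | 1.058 | 0.1836 + 0.0013 = 18.5% |

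At the ends of the tumor range, the same three pairs give 5.3%, 7.4% and 14.9% for n = 60, and 5.4%, 9.1% and 22.1% for n = 100.

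That formula tests a continuous correlation, whereas the protocol names group tests. A simulation of highest against lowest allium quartile (3000 runs per setting, true effect zero) comes closer. With both correlations at 0.2 in size, the unadjusted t-test rejects in 5.6% (60 tumors) and 6.4% (100 tumors). With both at 0.3 it rejects in 8.8% and 12.6%, and the spurious difference is about 0.22 SD. Adding the Western-diet score as a covariate brings the rate to 4.7% to 5.3% in these four settings. The simulated score is free of measurement error, which a questionnaire score will not be.

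**3. If the same unadjusted approach were used for blood IGF-1**

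Section 1.1 plans IGF-1 measurement in the study population, with targets of 1000 cases and 1000 controls. The same formula and assumed range give 9.7% to 97% for n = 1000 and 14.5% to nearly 100% for n = 2000. These rates are conditional on a method the protocol does not state.

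**The case against.** The strongest reply is that the protocol never calls these analyses unadjusted. ANOVA can carry further factors, Mantel-Haenszel methods can be stratified, and covariates for an exploratory question are often left to an analysis plan. This stands in part: naming a family of tests does not forbid adjustment. But section 5.4.3 does state methods, and it attaches control of confounding to one set of analyses and not to this one. The text as written therefore points to comparisons on diet alone.

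The second reply is that the confounding is assumed. That stands. The Introduction lists meat, animal fat and allium vegetables as separate risk associations. It does not say that men high in one are low in the other, and section 1.2.5 mentions neither meat nor fat. With zero correlation there is no bias.

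The third reply is that the effect is small where tests are actually named. With about 80 tumors the excess starts near nothing. A tissue marker also lies one step beyond blood IGF-1, so its correlation with diet may be weaker. If IGF-1 and marker correlate at 0.5 (assumed), the spurious correlations halve to between -0.01 and -0.06, and the rate is about 5% to 8%.

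The fourth is that the question is marginal. It closes a rationale section, is worded as exploration, and is not among the section 1.1 objectives. That also stands, but exploratory status does not remove a directional bias.

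A reader might infer that a vegetable with no effect would usually test as an inhibitor, citing the rates for 1000 or 2000 men. The documents do not support this: they fix no test of allium intake against blood IGF-1 and report no inverse relation between allium intake and Western diet.

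**Conclusion.** The point holds in a limited form. The tests named for tissue markers against diet cannot separate inhibition by allium vegetables from a less Western diet, and the protocol itself says that a Western-style diet raises IGF-1. An apparent allium effect can therefore be an artefact; the documents do not show that it will be.

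For about 80 tumors the false-positive rate is roughly 5% to 18% at a nominal 5%. This rests on the assumed correlations and on no adjustment being made. For blood IGF-1 the risk would be larger under the same approach, but the method there is open. The matter is confined to one exploratory question, and the primary genotype-risk analysis is untouched. The change is worth making mainly because it is cheap.

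**What to change.** In section 5.4.3, add a sentence for this exploratory question:

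- Fit a linear model (log or rank scale if skewed) of IGF-1, IGFBP3 and each tissue marker on allium intake.
- Adjust for the Western-diet components that the questionnaire holds (such as meat and animal fat, if collected), age, race, body mass index and smoking.
- Base any statement about inhibition on the adjusted allium coefficient, and report the crude comparison beside it.

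This also supplies the missing method for blood IGF-1.

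**Cost.** Some wording and one regression per marker, with no new samples or recruitment. With one parameter each for allium, meat, animal fat, age, race, body mass index and smoking, plus the intercept, the model uses 8 parameters. That leaves 60 − 8 = 52 to 100 − 8 = 92 residual degrees of freedom in the tumor set. The dietary items should first be checked against the questionnaire. If meat and fat were not asked, the text should say that dietary pattern cannot be separated out. Even with those items, error in reported diet leaves some residual confounding, so a cautious reading remains appropriate.
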